 - Once a patient has had a safety event, they will be censored from the analysis of that event only. For example, a patient for whom an endometrial hyperplasia outcome is identified will remain in follow-up for analysis of breast cancer (and endometrial cancer).
- End of the study period.
 - Patients will be censored by the end of the study period for each interim report and the final study report, however, additional follow-up time for these patients will be added during the subsequent study year.
- Occurrence of any type of cancer diagnosis;
 - As described in [Section 7.7.4](#), sensitivity analyses exploring the impact of this criterion will be performed.
- Hysterectomy;
 - Codes indicating a procedure for hysterectomy will be used to define this censoring criterion.
 - Presence of a code indicating post hysterectomy status (ICD-9-CM V88.01) or a hysterectomy procedure code at any time in the baseline or follow-up period will result in exclusion of the patient. The one exception is, when in the follow-up period, the procedure code precedes the hysterectomy status code (i.e., date of post-index hysterectomy is known); the patient's follow-up will be included, but censored on the procedure date.
- Death.

Discontinuation and/or resumption of *Duavee* or E+P HRT treatment will be defined and recorded, but follow-up will not be censored based on treatment discontinuation. Sensitivity analyses will be conducted to examine the impact of censoring based on (1) treatment switch and (2) cancer diagnosis. The Sponsor will also conduct sub-analyses for patients not included in the main analyses. These patient groups are those with either (1) use of E+P HRT (i.e., not new initiators), or (2) unopposed estrogen in their baseline period.

For each of the 4 study years, the Sponsor will: (1) identify and follow new *Duavee* or E+P HRT users; and (2) extend the follow-up to include newly available data covering any additional follow-up period for patients that were identified during previous study years.

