7.3. Variables and Measurement

7.3.1. Exposure

The analyses will identify exposure to *Duavee* or E+P HRT treatment based on pharmacy claims with applicable Generic Product Identifier (GPI) codes. A list of included products and the GPI codes is provided in Appendix 2.

E+P HRT comparator products were chosen and must have been commercially available in the US with an indication for the treatment of moderate to severe VMS associated with menopause or the prevention of postmenopausal osteoporosis.

The analyses will define exposure to *Duavee* or E+P HRT as follows: Patients will be categorized as having “current use” for *Duavee* or E+P HRT from their index date through to 30 days after the date when the supply of their last consecutive prescription is calculated to have been used. Prescriptions will be defined as consecutive if not more than 30 days has passed between the days supply of two adjacent prescriptions. Otherwise, a new treatment segment will be defined. The 30-day grace periods allow for the possibilities of intermittent inconsistent use and saving of dispensed pills, by which a patient may still be taking the medication even after exhausting the available supply from their most recent dispensing. For each patient, duration of exposure will be based upon the summation of recorded supply (in days) across all of their study treatment segments. Multiple treatment segments due to intermittent HRT use will be summed when calculating duration of exposure. The study will measure each exposure segment that occurs during the follow-up period in order to support analyses that consider duration of exposure and time since most recent exposure (defined as time from date of treatment end to censoring). Patients with long periods of follow-up that contain multiple treatment segments will be reflected in the variables of duration of exposure and time since most recent exposure.

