7.3.4. Covariates

The study will identify and describe the following variables prior to initiation of *Duavee* or comparator E+P HRT treatment. Applicable operational definitions, including International Classification of Diseases, 9th Revision, Clinical Modification (ICD-9-CM) diagnosis, ICD-9-CM procedure, Current Procedural Terminology (CPT) and Healthcare Common

Procedure Coding System (HCPCS) codes used to identify each variable are shown in Appendix 2.

Patient characteristics:

- Age;
- US region of residence;
- Year of cohort entry (ie, index date); and
- Duration of health plan eligibility prior to cohort entry (in months)

Medical conditions diagnosed during the baseline period:

- Vasomotor symptoms;
- Obesity;
- Osteoporosis;
- Cerebrovascular disease;
- Hyperlipidemia;
- Hypertension;
- Breast pain
- Benign breast lumps (fibrocystic nodule)
- Diabetes;
- Renal disease;
- Osteoarthritis;
- Major depression;
- History of CHD
- History of gallbladder disease;
- History of thyroid disease;
- Family history of cancer;

- At least one diagnosis code indicative of a prior safety event of interest (exclusive of cancers as this is a baseline exclusion criterion).

Use of prescription medications during the baseline period prior to the start of *Duavee* or E+P HRT:

- Corticosteroids;
- Lipid lowering agents;
- Antihypertensives;
- Antidepressants;
- Sedatives/hypnotics;
- Anticonvulsants;
- Antimycobacterials;
- Macrolides;
- Antifungals;
- Antivirals;
- Antidiabetics;
- History of oral contraceptive use;
- History of intrauterine device (IUD) exposure; and
- Unopposed estrogen HRT
- Selective estrogen receptor modulators (SERMs)
- Testosterone
- Local hormone treatments

Additionally, the analyses will describe the most frequently occurring diagnoses and medications seen during the baseline period, the reasons that follow-up was censored and characteristics of medication use during the follow-up period, specifically duration of therapy and time since most recent exposure (measured at the time of censoring from study).

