7.7.1. Main Analyses

The analyses will describe patients that initiate *Duavee* and the comparator E+P HRT cohort with respect to demographic and clinical characteristics as enumerated in [Section 7.3.4](#). Reasons for censoring will also be described by exposure group. Descriptive comparisons of the two cohorts will be done to document their differences at baseline and to identify potential confounders to be addressed in the propensity matching.

For each of the primary endpoints (i.e., endometrial hyperplasia and endometrial cancer), an IR will be calculated as the number of women meeting a claims-based algorithm for each outcome (first event only) divided by person-time at risk.

The IR and its associated 95% CI will be presented for each cohort overall and stratified by categorical patient age at cohort entry, total duration of *Duavee* or E+P HRT treatment (long vs. short), time since last exposure to *Duavee* or E+P HRT, exposure to local hormone therapy (See Appendix 2), and by presence (Y/N) of an osteoporosis diagnosis within the 90 days before or after initiation of *Duavee* or E+P HRT. Duration of treatment and time since last exposure will be categorized based on observed data distributions. The feasibility of these stratifications and of a possible analysis that stratifies simultaneously by duration of treatment and time since last exposure will be determined based on the number of observed safety events.

Further details of the validation process are described in Appendix 3 and will be contained in the separate Endpoint Algorithm Development Report.

Hazard ratios will be estimated that represent the relative risk associated with initiating *Duavee* as compared to E+P HRT. It is planned to conduct both crude (unadjusted) and adjusted analyses to assess the HR for each of the primary endpoints. Adjusted analyses will use propensity score matching to ensure comparability between treatment groups. Further discussion of the methods to be used in computing propensity scores is included in [Section 7.7.3](#).

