7.7.5. Additional Analysis Specifications

Since the analyses will employ a time-to-1st event analysis for the safety endpoints, there will not be a discrete risk window; rather the time from index drug exposure to the onset of the safety endpoint will be explored. The risk will be conditional on the duration of exposure to HRT and time since last exposure.

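### Incidence rates are stratified by treatment duration and time since last use as they stand at censoring, which builds immortal time into the stratified rates

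*Protocol*

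**What the plan says.** Section 7.3.1 defines recency as "time since most recent exposure (defined as time from date of treatment end to censoring", and states that "duration of exposure will be based upon the summation of recorded supply (in days) across all of their study treatment segments". Each is therefore one number per woman, complete only when her follow-up ends. Section 7.3.4 says the same of the medication-use variables: "specifically duration of therapy and time since most recent exposure (measured at the time of censoring from study".

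Section 7.7.1 then presents the primary-endpoint incidence rates by, among other factors, "total duration of *Duavee* or E+P HRT treatment (long vs. short), time since last exposure", with cut-points taken from the data: "Duration of treatment and time since last exposure will be categorized based on observed data distributions". Section 7.7.2 repeats these strata for women with earlier HRT use, and Section 7.7.6.2 lists them again. Section 7.7.5 adds: "The risk will be conditional on the duration of exposure to HRT and time since last exposure". It names no model and does not say that the values change over time.

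Women stay in follow-up after stopping: "follow-up will not be censored based on treatment discontinuation" (Section 7.1). No section says that a woman's person-time is divided as her duration or recency changes.

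**The concern.** A woman can be a long user only if she first remains event-free and under observation past the cut-point. If her whole follow-up is then labelled long, the early period, in which an event would have made her a short user, enters the long-use denominator with no possibility of an event in the numerator. Recency works the same way. An event ends follow-up for that endpoint and so stops the clock on time since last use. Women who end in the distant stratum bring with them all their earlier on-drug and recently-off-drug time, free of events by construction.

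The result is a gradient that does not depend on the drug: lower rates with longer use, and higher rates in current or recent users. For endometrial endpoints with an oestrogen-containing product, a reader of the reports could take the first as reassurance about prolonged use, or the second as an acute effect. A real increase in risk with duration could be masked.

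**Working it through.** The plan gives no figure for this point, so there is none to reproduce. The check asks what the rule returns when the true rate is the same in every stratum.

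**Inputs from the protocol.** Hyperplasia rate in E+P users at the third annual report (Table 1): λ = 399 / 89,438 = 0.00446 per year. Mean treatment 10 months (Table 1, footnote a), a stopping rate of 12/10 = 1.2 per year. Study length 4 years (Section 7.1).

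**Assumptions.** Constant hazard, no drug effect; exponential treatment duration in one continuous segment; entry uniform over the 4 years; disenrolment 0, 0.2 or 0.4 per year.

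**One case by hand: 12-month cut, no disenrolment, ignoring the small follow-up lost to events.**
- Share of women whose intended use exceeds 1 year: exp(−1.2) = 0.301.
- Time beyond month 12 per such woman: ∫₁⁴ (1 − t/4) dt = 1.125 years. Only events in this time can be classed as long: 1.125λ.
- Person-time credited to long: ∫₁⁴ t/4 dt = 1.875 years. The excess, 0.75 year, is the immortal first year of the 75% of women with more than a year of potential follow-up.
- Long rate: (1.125/1.875)λ = 0.60λ = 2.68 per 1,000 person-years.
- All women: 2.0 years and 2.0λ events each. Short rate: (2.0 − 0.301 × 1.125)λ / (2.0 − 0.301 × 1.875) = 1.661λ / 1.436 = 1.157λ = 5.16 per 1,000.
- Long/short ratio: 0.60 / 1.157 = 0.52. The truth is 1.0.
- With person-time split at month 12, the long denominator is 0.301 × 1.125 and the short denominator is 2.0 − 0.301 × 1.125. Each rate is then exactly λ and the ratio is 1.0.

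**Full range, by numerical integration with follow-up lost to events included (long/short ratio):**

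| Cut-point | Disenrolment 0 | 0.2 per year | 0.4 per year |
|---|---|---|---|
| Median duration (5.7, 5.0, 4.5 months) | 0.62 | 0.58 | 0.55 |
| 10 months | 0.55 | 0.51 | 0.47 |
| 12 months | 0.52 | 0.48 | 0.44 |

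Splitting person-time returns 4.46 per 1,000 in both strata in every cell. Simulations of 8 million women per scenario agree within sampling error.

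**Time since last use at censoring (rate per 1,000 person-years, truth 4.46 throughout):**

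| Stratum | Disenrolment 0 | 0.2 per year | 0.4 per year |
|---|---|---|---|
| Still on drug | 17.7 | 13.7 | 11.5 |
| Stopped, up to 12 months | 9.5 | 7.3 | 6.0 |
| Stopped, over 12 months | 1.96 | 1.83 | 1.72 |

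The first row barely changes if it is widened to one month after last use (17.6, 13.6, 11.4). By hand, with no disenrolment: a woman contributes on average ∫₀⁴ (1 − t/4)e^(−1.2t) dt = 0.661 years on drug and 0.661λ on-drug events, but only ¼∫₀⁴ t e^(−1.2t) dt = 0.165 year stays in the current-user denominator. The rate is 0.661λ / 0.165 = 4.0λ, about 17.8.

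**Between cohorts within a stratum, still with no effect.** If mean use is equal, the Duavee/E+P rate ratio is 1.00 in both strata. If mean use on Duavee is 8 or 14 months against 10, with a 6-month cut, the short-stratum ratio is 0.94 to 0.95 or 1.11 to 1.12. The long-stratum ratio stays at 1.00.

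**What is untouched.** The overall incidence rate divides all events by all person-time, with no classification. The main Cox contrast assigns exposure at the index date. Neither uses a value known only at the end of follow-up.

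**The case against.** The strongest reply is that the protocol does not compel the faulty calculation. Section 7.7.1 does not say whether women or person-time are allocated to strata. The wording in Section 7.3.4 sits in a sentence about description. Section 7.3.1 records every exposure segment precisely to support duration and recency analyses, and a statistical analysis plan may split the time properly. This makes the fix easy, but it does not remove the point. Section 7.3.1 itself defines recency as running to censoring, and Section 7.7.1 speaks of total duration. A programmer who follows those definitions has one value per woman.

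The second reply concerns weight, and it stands. These are secondary stratified rates, and Section 7.7.1 makes them subject to feasibility. Events will be few: 10/12 × (1,800 + 3,600 + 5,400) = 9,000 Duavee person-years, the figure that reproduces the third-report hyperplasia interval in Table 1 to within 0.01, gives about 9,000 × 399/89,438 = 40 hyperplasia and 9,000 × 80/89,438 = 8 cancer events. The study compares Duavee with E+P, and that comparison largely cancels the bias when durations of use are similar.

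Three stronger readings are tempting, and the protocol does not support them.
- A reader might infer that the main hazard ratio carries immortal-time bias. It does not, because exposure is fixed at initiation.
- A reader might infer that the absence of a current-use hazard ratio is an error that hides on-treatment risk. Ten months of use over 89,438/50,350 = 1.78 years of mean E+P follow-up is about 47% of time on drug, so an on-treatment ratio of 2.0 would read about 1 + 0.47 = 1.47. That holds only if excess risk ends when treatment stops, which the protocol does not state. Section 7.7.1 openly targets the risk associated with initiating treatment, Section 7.9 notes long cancer latency, and Section 7.4 already plans an exploratory analysis of event timing relative to treatment.
- A reader might put the osteoporosis stratum, which uses codes up to 90 days after initiation, in the same class. At most 90 days are immortal. With assumed baseline prevalence of 5% and post-index coding of 0.1 to 0.3 per year, the distortion was about 2 to 4%.

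**Conclusion.** As written, the stratification rule gives wrong rates. With no drug effect, long users would appear to have roughly 40 to 55% lower rates than short users (ratio about 0.44 to 0.62), and the rate would fall from about 11 to 18 per 1,000 person-years in current users to about 2 beyond a year off treatment, against a true 4.46 throughout. The sizes rest on exponential use with mean 10 months, uniform entry and the disenrolment range shown. The direction does not depend on these choices, and rarity of events does not remove the bias, because it comes from misallocated person-time.

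The error is confined to the duration and recency strata in Sections 7.7.1 and 7.7.2 and to any model under Section 7.7.5 that conditions on the fixed values. It should be fixed, but it does not threaten the primary comparison. A current-use hazard ratio and a pre-index osteoporosis definition are optional additions, not corrections.

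**What to change.** In Sections 7.3.1, 7.3.4, 7.7.1, 7.7.2 and 7.7.5, define cumulative duration of treatment and time since last exposure as time-updated quantities, each evaluated at the current day of follow-up. Split every woman's follow-up at the category boundaries using the exposure segments that Section 7.3.1 already records. Assign each event and each person-year to the category in force on that day. Enter the variables as time-varying terms in any Cox model that conditions on them. Bring the strata listed in Section 7.7.6.2 into line. Totals at censoring can stay in the tables that only describe medication use, provided they do not define rate strata.

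The cost is a few sentences and some programming. No new data are needed, and the overall rates and initiator hazard ratios do not change.

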7.7.2. Sub Analyses

Women with a previous history of E+P HRT use, different from their index drug (i.e., *Duavee* or specific E+P HRT) require special analytic considerations. In a new-user cohort design (as in the main analysis), these types of patients are excluded for several reasons. First, if women with past use of HRT incur a study endpoint, it is difficult to determine whether the endpoint is due to previous HRT or current HRT use. Further, women for whom previous HRT use was associated with poor outcomes (e.g., adverse effects) are likely to be under represented among those initiating *Duavee* or E+P HRT, which would deplete susceptible women and result in a survivorship bias or could lead to channeling of these

patients to one study drug over the other. Finally, baseline factors of women with previous use of HRT (e.g., comorbidities) could include effects of HRT (e.g., uterine bleeding) that could be intermediate in the causal pathway between exposure and study endpoints (e.g., endometrial hyperplasia, endometrial cancer). Controlling for factors that are intermediate in the causal pathway under study is to be avoided as it can invalidate a given analysis. Because of these limitations, analyses of the primary and secondary endpoints among *Duavee* and E+P HRT exposed patients with a previous history of HRT use will be limited to estimation of IRs and their associated 95% CI for each cohort overall and stratified IRs by the variables listed in the main analyses (patient age, treatment duration, time since last exposure, and exposure to local hormone therapy). These stratified analyses will only be done once there are at least 4 events in both the *Duavee* and E+P HRT groups.

New initiators of either *Duavee* or (E+P) HRT with evidence of unopposed estrogen therapy (i.e., estrogen HRT use without progestin use) in their baseline period, and no evidence of a hysterectomy, are not included in the main analyses. Patients with evidence of progestin use at anytime in their baseline period will not be categorized as having unopposed estrogen use. This group will be analyzed separately, because of the high likelihood of confounding by indication for the relationship of choice of study drug and the endometrial safety endpoints, and limitations of the data to identify hysterectomies that have occurred prior to a patient's baseline period. This results in an inability to accurately differentiate between patients with and without an intact uterus, both who have used unopposed estrogen. For a given safety endpoint, this analysis will only be done once there are at least four events in both the *Duavee* and E+P HRT groups.

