Study design: This PASS is a retrospective cohort study utilizing a US healthcare claims data source (HealthCore Integrated Research DatabaseSM [HIRD]). Two treatment groups of new initiators (*Duavee* and E+P HRT) will be defined and followed for each specified endpoint until the end of the study period or until that endpoint occurs. Other censoring events include hysterectomy, switch of index treatment, and disenrollment from the HIRD, diagnosis of cancer or death. The planned study will be 4 years in duration and will follow new initiators identified in 2014-2018.

Study Population: All patients identified in the HIRD who have received at least one prescription for *Duavee* or E+P HRT since May 2014 (US commercial launch date), and have a baseline period (e.g., 6 or 12 months to be determined by a priori analyses) prior to their first study medicine prescription, will be included in this study. Patients without a uterus and those with an existing cancer diagnosis will be excluded. Only new initiators will be included in the main analysis. To be a new initiator, patients need to have no recorded use of either *Duavee* or E+P HRT products in their baseline period. Patients with prior use of E+P HRT in either the *Duavee* or E+P HRT cohort will be excluded from the main analyses, but will be included in sub analyses. Similarly, patients with a history of unopposed estrogen use in their baseline period will be analyzed in sub analyses but excluded from the main analyses. Figure 4 in [Section 7.7](#) details the analysis populations.

Variables: Variables will be defined and analyzed that represent patient characteristics, comorbidities, utilized medications, medical history, and safety endpoints. A listing of study variables is provided in [Section 7.3.1](#).

Data source: The HIRD is a longitudinally integrated, US research database comprising payment claims for healthcare encounters among included health insurance plans. It is among the largest of its kind in the US and has been extensively used for pharmacoepidemiologic research, including many PASS.^{1,2,3,4}

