7.2.1. Inclusion Criteria

All patients identified in the HIRD who have received a prescription for *Duavee* or E+P HRT since May 2014 (date of first commercial availability in the US), and have a baseline period (e.g., 6 or 12 months to be determined by a priori analyses) prior to their first study medicine prescription, will be included in this study. Codes for *Duavee* and specific E+P HRT products are listed in Appendix 2.

- To be included in the main analyses, patients need to be new initiators of *Duavee* or E+P HRT as evidenced by a sufficient baseline period (e.g., 6 or 12 months to be determined using a priori analyses) prior to their first study drug prescription with no prior use of either *Duavee* or E+P HRT.
- The duration of the baseline period will be determined prior to the start of the analysis. The analysis will assess the distribution of continuous enrollment prior to the first dispensing of *Duavee* among the exposed patients. Selection of a threshold will balance inclusion of as many *Duavee* users as is feasible with the need to ensure appropriate capture of baseline covariates among the included patients.
- Sub-analyses will be performed for those with either (1) use of E+P HRT (i.e., not new initiators), or (2) unopposed estrogen in their baseline period. See Figure 4 in Section [Section 7.8](#) for the flow of patients to the separate analyses.

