7.2.2. Exclusion Criteria

Patients meeting any of the following criteria will be excluded from the study:

- Patients with an insufficient period of enrollment prior to their index prescription (e.g., 6 or 12 months as determined prior to the start of analysis) will be excluded. This period is necessary to determine if the patient is a new initiator of *Duavee* or E+P HRT without a history of unopposed estrogen use, and also to adequately ascertain baseline covariates/patient history;
- Patients without a uterus, i.e., males, or women for whom evidence of hysterectomy is identified prior to initiation of *Duavee* or comparator E+P HRT; and
- Patients with a history of any type of cancer in their baseline period.
- Patients for whom *Duavee*, comparator E+P HRT or unopposed estrogen are identified during the baseline period will be excluded from the main analyses. They will be evaluated in separate sub-analyses.

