- Sub analyses of prevalent users of unopposed estrogen may be difficult to interpret due to selection factors and unmeasured covariates. We anticipate that this group will include
 1. Patients with an intact uterus with past use of unopposed estrogen,
 2. Patients without a uterus for whom no hysterectomy was identified in the automated claims data due to timing of the procedure, and
 3. Patients who used both estrogen and sporadic progesterone for whom a progesterone dispensing was not observed.

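### As written, a woman using systemic estrogen with a separately dispensed progestin at baseline meets no main-analysis exclusion and would count as a new initiator

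*Protocol*

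**What the plan says.** The exclusion rule in 7.2.2 reads: "Patients for whom *Duavee*, comparator E+P HRT or unopposed estrogen are identified during the baseline period will be excluded from the main analyses". The Abstract defines the new user in the same terms: "To be a new initiator, patients need to have no recorded use of either *Duavee* or E+P HRT products in their baseline period".

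Section 7.3.1 says how such use is found: "The analyses will identify exposure to *Duavee* or E+P HRT treatment based on pharmacy claims with applicable Generic Product Identifier (GPI) codes". It continues: "A list of included products and the GPI codes is provided in Appendix 2". The cohort-defining table in Appendix 2 names Duavee and eight comparator brands. Each of the eight contains both an estrogen and a progestin; no separate estrogen or progestin is listed there.

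Section 7.7.2 defines unopposed estrogen therapy as estrogen HRT without a progestin and then narrows it: "Patients with evidence of progestin use at anytime in their baseline period will not be categorized as having unopposed estrogen use". It does not say to which group such women then belong.

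The same section explains why past HRT users are kept out of the main analysis. An endpoint cannot be attributed to earlier or current use, susceptible women are depleted or channeled to one drug, and baseline factors may already be effects of HRT.

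**The concern.** The new-user design rests on the baseline screen. If the screen recognizes prior combined therapy only when it was dispensed as one listed product, established users of two-product regimens pass as new. Each reason in 7.7.2 for keeping prior users out applies to them as well. At stake is the composition of both main cohorts for the primary endometrial endpoints. If the share of such women differs between Duavee and E+P initiators, part of the HR would reflect earlier hormone exposure.

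Follow-up is handled more strictly than baseline. Section 7.1 censors at any estrogen product differing from the index regimen, which limits concurrent use after the index date. It does nothing about exposure before that date.

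**Working it through.** **Step 1: apply the rules as written.** A woman is excluded if, in the baseline period, she has Duavee, or a listed E+P product, or estrogen with no progestin.

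| Baseline dispensing | Duavee? | Listed E+P? | Unopposed estrogen? | Result |
|---|---|---|---|---|
| None | no | no | no | main analysis |
| Listed combined product | no | yes | no | excluded |
| Estrogen only | no | no | yes | excluded |
| Estrogen and separate progestin | no | no | no (7.7.2) | main analysis |

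One progestin fill at any time in the baseline period (6 or 12 months, still to be chosen) is enough to move an estrogen user from the third row to the fourth.

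**Step 2: check whether adjustment closes the gap.** The covariates in 7.3.4 include unopposed estrogen HRT and local hormone treatments, but no item for systemic estrogen with a separate progestin. Section 7.7.3 builds the propensity score from prescription data broadly, so partial adjustment is possible but not assured.

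**Step 3: illustrate the size.** The protocol has no figure to reproduce on this point. Let pD and pE be the shares of such women among Duavee and E+P initiators, and r their endometrial event rate relative to true new users. Assume that r and the true HR are the same throughout. The average rate in each cohort is then scaled by 1 + p(r − 1), so the crude HR is multiplied by

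[1 + pD(r − 1)] / [1 + pE(r − 1)].

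All values of p and r below are assumptions.

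| pD | pE | r = 0.5 | r = 2 |
|---|---|---|---|
| 5% | 5% | 1.00 | 1.00 |
| 20% | 10% | 0.90/0.95 = 0.95 | 1.20/1.10 = 1.09 |
| 30% | 10% | 0.85/0.95 = 0.89 | 1.30/1.10 = 1.18 |

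Reversing the shares inverts the ratios. With 10% versus 30%, the multiplier is 0.95/0.85 = 1.12 at r = 0.5 and 1.10/1.30 = 0.85 at r = 2. The direction is therefore open.

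**Step 4: set this against the planned precision.** For hyperplasia at the third report with a true HR of 1.0, Table 1 projects 0.72 to 1.39. The multipliers lie inside that interval. A shift of 1.18 would still raise the upper limit, which the protocol uses as the HR it can rule out, to 1.39 × 1.18 = 1.64.

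**The case against.** The best defense is that the protocol means E+P HRT broadly. Section 7.7.2 speaks of past HRT use in general. Section 7.1 refers to a single-unit E+P HRT, a qualifier that would be redundant if the term covered only single products. The Appendix 2 table defines the index drugs, and the appendix calls its codes candidates. Read this way, the progestin sentence merely sorts opposed from unopposed users, and the opposed ones go to the prior-HRT sub-analysis. Figure 4, which would show the flow, is not available.

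This makes it plausible that exclusion was intended. It does not show that the text achieves it. Section 7.2.2 says comparator E+P HRT, the Abstract says E+P HRT products, and 7.3.1 ties identification to the product list. The progestin rule is body text, not a provisional code. If Figure 4 differs, it conflicts with these sections and they still need aligning.

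A reader might also take 7.9 as evidence that such women are in the main cohort, since it anticipates "Patients who used both estrogen and sporadic progesterone for whom a progesterone dispensing was not observed". It is not. Those women keep the unopposed label and stay out of the main analysis. The passage shows only that the sponsor expects combined use of separate products.

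The objection to the size stands in full. No share or rate ratio comes from the protocol, the formula is for the crude HR, and propensity score matching with doubly robust estimation may remove part of the effect.

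**Conclusion.** The gap in the stated rules is real: a baseline user of systemic estrogen with a separately dispensed progestin meets no main-analysis exclusion and is assigned to no sub-analysis. This conflicts with the protocol's own case for a new-user design. The conclusion rests on the text of 7.2.2, 7.3.1, 7.7.2 and Appendix 2, and is subject to Figure 4.

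A reader might go further and infer that the primary HR will be biased, or biased in a known direction. The protocol does not support that. The distortion is nil with equal shares. The range of about 0.89 to 1.18 holds only for the assumed shares of 20–30% versus 10% and rate ratios of 0.5 to 2, before adjustment. The correction should be made because it is short and protects the design, not because a material bias has been shown.

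**What to change.** - In 7.2.2 and 7.7.2, state that any systemic estrogen dispensing in the baseline period, with or without a separately dispensed progestin, excludes a woman from the main analysis.
- Assign women with a progestin fill to the prior-HRT sub-analysis and the rest to the unopposed-estrogen sub-analysis.
- Add the systemic estrogen and progestin codes to Appendix 2 and align Figure 4. Limiting the rule to systemic estrogen leaves local hormone therapy where 7.7.1 has it, as a stratifier within the main analysis.

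The text change is small, and under the Milestones section the analytic dataset is extracted only after protocol approval. The real cost is precision, in proportion to the share of such women. At the assumed 20–30% of the 1,800 Duavee initiators projected for the first report, 360 to 540 would leave the main cohort. Because Duavee events dominate the variance, the CI on the log scale would widen by a factor of roughly 1/√0.8 = 1.12 to 1/√0.7 = 1.20. If the share is small, both this cost and the bias avoided are small.
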